6.2 Randomization

The randomization sequence will be obtained by computer-generated random numbers and provided to each HVTN CRS through the Statistics and Data Management Center's (SDMC) Web-based randomization system. The randomization will be done in blocks to ensure balance across study groups. At each institution, the pharmacist with primary responsibility for dispensing study products is charged with maintaining security of the treatment assignments.

6.3 Blinding

This is an open-label study. Participants and site staff will be unblinded to participants' group assignments. Laboratory program staff will be blinded to participants' group assignments during assay analysis, whenever feasible.

6.4 Statistical analyses

This section describes the final study analysis. All data from enrolled participants will be analyzed according to the initial randomization assignment regardless of how many vaccinations they received. The analysis is a modified intent-to-treat analysis in that individuals who are randomized but not enrolled do not contribute data and hence are excluded. Because of the brief length of time between randomization and enrollment—typically no more than 4 working days—very

few such individuals are expected. All analyses will be performed using SAS and R.

No formal multiple comparison adjustments will be employed for multiple safety endpoints, multiple primary immunogenicity endpoints, or secondary endpoints. However, multiplicity adjustments will be made for certain immunogenicity assays, as discussed below, when the assay endpoint is viewed as a collection of hypotheses (eg, testing multiple peptide pools to determine a positive response).

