1.5 Study plan and schema table

Participants will be evaluated for safety and immune responses through blood collection at specified timepoints throughout the study. The study schema is below:

Table 1-1 Schema

Group	N	Product/Dose	Route	Injection Schedule			
				Month 0	Month 1	Month 3	Month 6
1	10	INO-6160 / 2.0 mg	ID EP	X	X	X	X
2	10	INO-6160 / 2.0 mg	ID EP	X	X	X	X
		Trimer-4571 / 100 mcg 3M-052-AF (5 mcg) + Alum (500 mcg)	IM	--	--	X	X
Total	20*						

Table 1-1 Notes: The dose of INO-6160, 2 mg, will be administered as 2 separate intradermal (ID) injections because of the volume limitation of the device for intradermal injection. Each of 2 sites will receive 0.1 mL via ID injection (Mantoux injection) bilaterally, one on each upper arm. Following ID injections, EP will be performed with the Inovio CELLECTRA 2000 device. The dose of Trimer 4571, 100 mcg, will be administered as 2 injections delivered intramuscularly (IM) via needle and syringe in both deltoid muscles. For all injections, if administration into the deltoid is contraindicated, the thigh muscle can be used (see Section 7.3.4).

* Up to 5 additional participants may be enrolled (for a total of 25), if needed, with a goal of approximately 20 participants to contribute to the immunogenicity analyses. Specific scenarios that could necessitate enrollment of additional participants in order to prevent loss of statistical power of the study include (but are not limited to) the following: loss of participants due to moving, withdrawal of consent, missing vaccine visits, or variations in the clinical care due to unpredictable events. Participants will not be replaced after visit 5, the visit 2 weeks post second vaccination, and replacement will require the assent of Protocol team leadership.

Enrollment will be restricted to 1 participant per day for the first 5 participants (**across both arms**) and enrollment will pause after the first 5 participants are enrolled. The Protocol Safety Review Team (PSRT) will review cumulative safety information for all participants recorded through the visit scheduled 2 weeks post first vaccination for the first 5 participants and will determine whether it is safe to proceed with full enrollment.

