5.2.3 Participant departure from vaccine schedule

If a participant misses a scheduled vaccination, they are still eligible to receive future vaccinations.

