6.4.1 Analysis variables

The analysis variables consist of baseline participant characteristic, safety, and immunogenicity for primary- and secondary-objective analyses.

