6.4.3 Safety/tolerability analysis

Since enrollment is concurrent with receiving the first vaccination, all participants will have received at least 1 vaccination and therefore will provide some safety data.

Reactogenicity: The number and percentage of participants experiencing each type of reactogenicity sign or symptom will be tabulated by severity and treatment. For a given sign or symptom, each participant's reactogenicity will be counted once under the maximum severity for all injection visits. Wilcoxon rank sum tests will be used to test for differences in severity between groups.

AEs and SAEs: AEs will be coded into Medical Dictionary for Regulatory Activities (MedDRA)–preferred terms. The number and percentage of participants experiencing each specific AE will be tabulated by severity and relationship to study vaccine. For the calculations in these tables, each subject's AE will be counted once under the maximum severity or strongest recorded causal relationship to treatment. A complete listing of AEs for each subject will provide details including severity, relationship to treatment, onset, duration, and outcome.

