## 8 IMMUNOGENICITY TABLES AND FIGURES, BY ASSAY

If any participants missed the IM administration at Month 3 in Group 2, the analyses of immunogenicity data collected at Visit 7 (2 weeks after the 3rd vaccination) will be done for all participants, and for the subset of participants who received the full Month 0, Month 1 and Month 3 vaccinations in both study groups. If any participants missed the IM administration at Month 6 in Group 2, the analyses of immunogenicity data collected at Visit 9 (2 weeks after the 3rd vaccination) and Visit 10 (6 months after the 4th vaccination) will be done for all participants, and for the subset of participants who received the full Month 0, Month 1, Month 3 and Month 6 vaccinations in both study groups.

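### Safety is tabulated only by randomised arm, with no table by dose or by product received, so Group 2 participants who never get Trimer 4571 would dilute the rates of post-boost events

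*Protocol*

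**What the plan says.** Section 6.4 sets one analysis population: "All data from enrolled participants will be analyzed according to the initial randomization assignment regardless of how many vaccinations they received". Section 6.4.1 puts safety under that rule: "The analysis variables consist of baseline participant characteristic, safety, and immunogenicity for primary- and secondary-objective analyses".

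Section 6.4.3 makes no exception. It notes that every enrolled participant has had at least one vaccination. On reactogenicity it says: "The number and percentage of participants experiencing each type of reactogenicity sign or symptom will be tabulated by severity and treatment". Each sign or symptom is collapsed over the whole schedule: each participant's "reactogenicity will be counted once under the maximum severity for all injection visits". Severity is compared between groups by a Wilcoxon rank sum test. Adverse events are tabulated by severity and relationship, with a full listing per participant.

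Trimer 4571 with its adjuvants is given only in Group 2, at Months 3 and 6 (Sections 1.5 and 7.1). The protocol foresees that some may not receive it. Section 5.2.2 lists grounds for permanent discontinuation. Section 5.2.3 says: "If a participant misses a scheduled vaccination, they are still eligible to receive future vaccinations". Section 1.5 says: "Participants will not be replaced after visit 5". Visit 5 is Day 43, and the first Trimer dose is due at Visit 6, Day 85 (Appendices A and B).

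For immunogenicity there are subsets by doses received: optional in protocol 6.4.4.2, and planned in SAP Sections 7 and 8. SAP Section 8 has a rule that begins "If any participants missed the IM administration at Month 3 in Group 2", and a matching one for Month 6. The SAP covers immunogenicity only.

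**The concern.** Primary objective 1 includes the safety of the DNA regimen combined with adjuvanted Trimer 4571. A Group 2 participant who stops before Month 3 has received only what Group 1 receives, yet counts in the Group 2 denominator and in the severity comparison with Group 1. For events that follow the boost, that participant adds to the denominator and cannot add to the numerator.

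Because reactogenicity is taken at its maximum over all injection visits, the planned tables also cannot separate a reaction to the DNA prime from one to the Trimer boost. With 10 per group, one or two people visibly change the rate a reader would take as the tolerability of the combination.

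**Working it through.** **1. Does any safety analysis by exposure exist?** Section 6.4 fixes the arm as randomised and 6.4.1 includes safety. The word treatment in 6.4.3 does not create an as-treated set, because Section 7.1 uses Treatment 1 and Treatment 2 as labels for the two group regimens. Section 6.1.2 says SAEs are monitored after each dose and pools both groups (n = 20) for the first two doses, but 6.4.3 carries no per-dose table or denominator forward. None was found elsewhere in either document.

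**2. Reproduce the plan's safety figures.**
- Event rate giving a 90% chance of at least one event: 1 − 0.1^(1/n). This gives 20.6% for n = 10 and 10.9% for n = 20, as in Section 6.1.2.
- Table 6-4 is reproduced by adding 2 successes and 2 failures: p = (x + 2)/(n + 4), limits p ± 1.96·√[p(1 − p)/(n + 4)], cut at 0. For 0/10: p = 2/14 = 0.143, upper limit 0.143 + 0.183 = 32.6%. For 0/20 it gives 19.4%. Both match.

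The figures for n = 10 take all 10 members of a group as exposed.

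**3. Let k be the number in Group 2 who never receive Trimer.** The documents do not give k, so it is an assumption, shown over a range. The exposed number is 10 − k. For an event possible only after Trimer, the as-randomised rate is the rate among the exposed times (10 − k)/10.

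| k | Exposed | Factor | Rate detectable with 90% chance | Upper 95% bound, 0 events | Chance of ≥1 event at a true 20% |
|---|---|---|---|---|---|
| 0 | 10 | 1.0 | 20.6% | 32.6% | 0.89 |
| 1 | 9 | 0.9 | 22.6% | 35.0% | 0.87 |
| 2 | 8 | 0.8 | 25.0% | 37.8% | 0.83 |
| 3 | 7 | 0.7 | 28.0% | 41.0% | 0.79 |

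With k = 2 and two such events, the table shows 2/10 = 20%; among those exposed it is 2/8 = 25%.

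**4. Illustration from the protocol's background data.** Section 2.4 reports Grade 3 systemic reactogenicity in 5 of 13 (38.5%) in HVTN 300, which used the same adjuvants with a different trimer at 300 mcg. Section 2.3.1 reports no severe systemic reactogenicity in the related DNA trials. If those rates applied here, the Group 2 figure would read 34.6%, 30.8% or 26.9% for k = 1, 2 or 3.

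**5. How likely is k ≥ 1?** The chance is 1 − (1 − q)^10, where q is the rate of non-receipt.
- Discontinuations over sample size in Table 2-1: 1/120, 2/48, 3/100 and 1/94. These give 8%, 35%, 26% and 10%.
- If q were 5% to 10%, the chance would be 40% to 65%. That is an assumption: the protocol's own 10% is a rate of missing immunogenicity data and includes shipping and cell-viability losses.

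**The case against.** The strongest reply is that primary objective 1 asks about a regimen: two DNA doses followed by two further doses, alone or combined. Analysis as randomised answers that question and preserves the basis of the between-group test. This stands, and it is why those tables should remain.

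A reader might infer that the rule can only understate risk in Group 2. The documents do not support that. A participant who never gets Trimer still contributes INO-6160 reactions. Someone stopped before Month 3 for a related Grade 3 event under Section 5.2.2 would raise the Group 2 rate. Dilution is also smaller for reactions that both products can cause.

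A reader might also infer that safety should switch wholly to product received, with unboosted Group 2 participants counted as DNA-only. That could reverse a signal. Suppose one Group 2 participant stops after a related Grade 3 event at dose 2 and no one else has such an event. As randomised this is 1/10 against 0/10. Pooled by product it becomes 0/9 against 1/11.

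There is partial mitigation. The adverse event listing gives onset and relationship, expedited reporting names INO-6160 and the adjuvanted Trimer separately (Section 9.2.1), and the PSRT reviews safety weekly until two weeks after the last injection. In an open-label trial of 20, exposed-only adverse event rates could be rebuilt by hand. But a listing is not a planned rate or denominator. The SAP's silence on safety subsets shows little, since safety is outside its scope.

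**Conclusion.** The gap is real but conditional: no safety table by dose or product received is planned beside the as-randomised ones. The effect is 10% relative per unexposed Group 2 participant, for events that can occur only after Trimer, assuming 10 in the group. It is nil if all 10 received Trimer. The SAP reports 10 enrolled per group but not how many were boosted, so the documents do not show that dilution occurred. The zero-event bounds of 32.6%, 35.0% and 37.8% follow the method behind Table 6-4; an exact interval would give 30.8% for 0/10, which is not the protocol's figure. Section 6.4.3 itself plans no safety confidence intervals. This is a cheap improvement to reporting and does not invalidate the planned safety analysis.

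**What to change.** Keep the as-randomised safety tables and the between-group severity test. Add to Section 6.4.3:

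- Reactogenicity tabulated by vaccination number, with participants who received the product at that vaccination as the denominator. For the combination at vaccinations 3 and 4, that means those given Trimer 4571 at that vaccination.
- Adverse events with onset on or after the first Trimer 4571 dose, among participants who received at least one Trimer dose. Set these beside Group 1 participants who received vaccination 3, with events counted from that vaccination.
- A statement that events before the boost stay in the as-randomised tables, that Group 2 participants not given Trimer are not pooled into Group 1, and that their number is reported.

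The cost is a received-product flag and a few extra tables, with no change to conduct or data collection. The boost-period denominator may be slightly smaller. The boost-period comparison is conditional on completing the prime, so it should be labelled descriptive and carry no test.

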6.4.1 Analysis variables

The analysis variables consist of baseline participant characteristic, safety, and immunogenicity for primary- and secondary-objective analyses.

6.4.2 Baseline demographics

Participants' baseline characteristics will be summarized using descriptive statistics.

6.4.3 Safety/tolerability analysis

Since enrollment is concurrent with receiving the first vaccination, all participants will have received at least 1 vaccination and therefore will provide some safety data.

Reactogenicity: The number and percentage of participants experiencing each type of reactogenicity sign or symptom will be tabulated by severity and treatment. For a given sign or symptom, each participant's reactogenicity will be counted once under the maximum severity for all injection visits. Wilcoxon rank sum tests will be used to test for differences in severity between groups.

AEs and SAEs: AEs will be coded into Medical Dictionary for Regulatory Activities (MedDRA)–preferred terms. The number and percentage of participants experiencing each specific AE will be tabulated by severity and relationship to study vaccine. For the calculations in these tables, each subject's AE will be counted once under the maximum severity or strongest recorded causal relationship to treatment. A complete listing of AEs for each subject will provide details including severity, relationship to treatment, onset, duration, and outcome.

6.4.4 Immunogenicity analyses

6.4.4.1 Statistical Analysis to address primary objectives

The first component of the analysis will entail comparing the frequency of HIV-1–specific binding Ab responses 2 weeks following the fourth vaccination. Comparison between the 2 vaccine groups will use Fisher's exact test, while

McNemar's test will be used for paired data (between visits), with a significant difference declared if the 2-sided p-value is ≤ 0.05 .

To compare the magnitude of HIV-1-specific binding Ab responses 2 weeks following the fourth vaccination. Between the 2 vaccine groups, a two-sided Wilcoxon rank sum test with 5% type-I error rate will be performed. Wilcoxon signed rank test with 5% type-I error rate will be performed for paired data.

With the response rates of CD4+ and CD8+ T cell to HIV-1 specific Env peptide pools 2 weeks following the fourth vaccination, the 2 vaccine groups will be compared using Fisher's exact test, and McNemar's test will be used for paired data), with a significant difference declared if the 2-sided p-value is ≤ 0.05 . For each T-cell subset, the positivity call for each peptide pool will include a multiple-comparison adjustment for the number of peptide pools used in the assay using the discrete Bonferroni adjustment. The magnitude of response will be analyzed with two-sided Wilcoxon rank sum test for independent data and Wilcoxon signed rank test for paired data, with 5% type-I error rate. Graphs will be used to display the background-subtracted magnitudes for each participant by protein, treatment arm, and timepoint, with a box plot of data from positive responders superimposed on the individual data values. Statistical testing comparing the magnitudes will be based on positive responders only.

6.4.4.2 General approach for secondary and exploratory analyses

For the statistical analysis of immunogenicity endpoints, data from enrolled participants will be used according to the initial randomization assignment regardless of how many injections they received. Additional analyses may be performed, limited to participants who received all scheduled injections per protocol. Assay results that are unreliable, from specimens collected outside of the visit window, or from HIV-infected participants are excluded. Since the exact date of HIV infection is unknown, any assay data from blood draws 4 weeks, or less, prior to an infected participant's last seronegative sample and thereafter may be excluded. If an HIV-infected participant does not have a seronegative sample post enrollment, then all data from that participant may be excluded from the analysis.

Discrete categorical assay endpoints (eg, response rates) will be analyzed by tabulating the frequency of positive response for each assay by antigen and treatment arm at each timepoint for which an assessment is performed. Crude response rates will be presented with their corresponding 95% CI estimates calculated using the score test method (38). Fisher's exact tests will be used to compare the response rates of between 2 vaccine groups, with a significant difference declared if the 2-sided p-value is ≤ 0.05 .

For quantitative assay data (eg, magnitude of HIV-1 Env-specific binding Ab responses), graphical and tabular summaries of the distributions by antigen, treatment arm, and timepoint will be made. The difference between arms at a specific timepoint will be tested with a nonparametric Wilcoxon rank sum test if

the data are not normally distributed and with a 2-sample t-test if the data appear to be normally distributed. An appropriate data transformation (eg, log10 transformation) may be applied to better satisfy assumptions of symmetry and homoscedasticity (constant variance). More sophisticated analyses employing repeated measures methodology (for example, repeated measures analysis of variance or generalized estimating equations) may be utilized to incorporate immune responses over several timepoints and to test for differences over time. However, inference from such analyses would be limited by the small sample size of this study. All statistical tests will be 2-sided and will be considered statistically significant if $p \leq 0.05$.

6.4.4.3 Missing Data

Based upon previous AIDS Vaccine Evaluation Group and HVTN trials, missing 10% of immunogenicity results for a specific assay is common due to study participants terminating from the study early, problems in shipping specimens, or low cell viability of processed peripheral blood mononuclear cells (PBMCs). To achieve unbiased statistical estimation and inferences with nonparametric tests and generalized linear models fit by generalized estimating equation (GEE) methods, missing data need to be missing completely at random (MCAR). MCAR assumes that the probability of an observation being missing does not depend upon the observed responses or upon any unobserved covariates but may depend upon covariates included in the model (eg, missing more among whites than nonwhites). When missing data are minimal (specifically if no more than 20% of participants are missing any values), then nonparametric tests and GEE methods will be used, because violations of the MCAR assumption will have little impact on the estimates and hypothesis tests. These models will include as covariates all available baseline predictors of the missing outcomes.

If a substantial amount of immunogenicity data is missing (at least 1 value missing from more than 20% of participants), then using the methods that require the MCAR assumption may give misleading results. In this situation, analyses of the immunogenicity endpoints at a specific timepoint will be performed using parametric generalized linear models fit by maximum likelihood. These methods provide unbiased estimation and inferences under the parametric modeling assumptions and the assumption that the missing data are missing at random (MAR). MAR assumes that the probability of an observation being missing may depend upon the observed responses and upon observed covariates, but not upon any unobserved factors. Generalized linear models for response rates will use a binomial error distribution and for quantitative endpoints, a normal error distribution. For assessing repeated immunogenicity measurement, linear mixed effects models will be used. If the immunological outcomes are left- and/or right-censored, then the linear mixed effects models of Hughes (39) will be used because they accommodate the censoring. In addition, secondary analyses of repeated immunogenicity measurements may be done using weighted GEE (40) methods, which are valid under MAR. All of the models described above will include as covariates all available baseline predictors of the missing outcomes.

6.4.5 Analyses prior to end of scheduled follow-up visits

Any analyses conducted prior to the end of the scheduled follow-up visits should not compromise the integrity of the trial in terms of participant retention or safety or immunogenicity endpoint assessments. In particular, early analyses by treatment assignment require careful consideration and should be made available on a need-to-know basis only.

6.4.5.1 Safety

During the course of the trial, analyses of safety data will be prepared approximately every 4 months for review by the Safety Monitoring Board (SMB). Ad hoc safety reports may also be prepared for SMB review at the request of the HVTN 304 PSRT. The HVTN leadership must approve any other requests for safety data prior to the end of the scheduled follow-up visits.

6.4.5.2 Immunogenicity

A statistical analysis by treatment assignment of a primary immunogenicity endpoint may be performed. The HVTN Laboratory Program will review the analysis report prior to distribution to the protocol chairs, Division of AIDS (DAIDS), vaccine developer, and other key HVTN members and investigators. Distribution of reports will be limited to those with a need to know for the purpose of informing future trial-related decisions. The HVTN leadership must approve any other requests for HVTN immunogenicity analyses prior to the end of the scheduled follow-up visits. Any analyses conducted prior to the end of the study should not compromise the integrity of the trial in terms of participant retention or safety or immunogenicity endpoint assessments.

7 Study vaccine preparation, storage, and administration

